4. Aim and Objectives

The aim of this study is to evaluate the effect of wearing custom-fitted mouthguards on the speech performance and oral impairment of the Malaysia national rugby players.

The specific objectives are :

- i. To compare the speech performance before, immediately after, one-week after, one-month after and six-month after wearing custom-fitted mouthguard;
- ii. To compare the level of oral impairment before, immediately after, one-week after, one-month after, and six-month after wearing custom-fitted mouthguard; and
- iii. To estimate the incidence of traumatic dental injury within the six-month custom-fitted mouthguards use period.

5. Research hypotheses

The null hypotheses are :

- i. Speech performance at various time points is not affected by wearing custom-fitted mouthguard;
- ii. Level of oral impairment at various time points is not affected by wearing custom-fitted mouthguard; and
- iii. No incidence of dental trauma occurs within the six-month custom-fitted mouthguards use period.

6. Methodology

An interventional study using single-arm pre- and post- design will be carried out at the National Sports Institute. All the national rugby players taking part in the Asia Rugby Championship Premier 2018 will be invited to participate in this study. The information sheet regarding the study will be given out while the objectives and conduct of the study will be explained to the players. All players who agreed to participate will need to provide written informed consent.

To be eligible for inclusion, the players must be:

- a) Men aged between 18 and 35;
- b) Actively playing rugby;
- c) Currently playing in Malaysia Rugby Union;
- d) Native speakers of Malay (national language), with the ability to read and write in Malay fluently;
and
- e) Without any history of either speech or hearing impairment.

The exclusion criteria are:

- a) Retired players;
- b) National players who did not play rugby within the last six months of the recruitment date; and
- c) Players with cleft lip and/or cleft palate; and

d) Players with any history of either speech or hearing impairment.

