The sample size was calculated using G*Power 3.1 software (available at <http://www.gpower.hhu.de/>). The assumptions was an effect size of 0.25 with a 5% margin of error. The power of the study 80% and there was a total of six repeated measurements. Correlation among the repeated measures was set at 0.5. This yielded a minimal sample size of 24. Considering that drop-outs are higher with long-term follow-up, the sample size was increased by 20% to $n = 30$.

Development of questionnaire to evaluate oral impairment

A questionnaire will be developed to evaluate any oral impairment that could be experienced by the subjects before and during the use of a mouthguard. The questionnaire will be divided into four parts: (i) demographic information such as gender, age, frequency and duration of playing, highest level of representation and experience wearing custom-fitted mouthguard, (ii) frequency of wearing mouthguard, (iii) problems arise during mouthguard use and (iv) general perception on mouthguard. All questions in part (ii), (iii) and (iv) will be formatted in a five-point Likert scale. The following ratings will be given for the different possible answers in part (ii) and part (iii) with a qualitatively ordinal character: “Never” = 1; “Rarely” = 2; “Sometimes” = 3; “Often” = 4; “Always” = 5. For part (iv), the possible responses were: “Strongly disagree” = 1; “Disagree” = 2; “Neutral” = 3; “Agree” = 4; “Strongly agree” = 5. The questionnaires will be printed in Malay, the national language of Malaysia.

This questionnaire set will be validated and pretested on 10 undergraduate dental students. The cognitive interview will be carried out while the students are completing the questionnaire. Face validity will be determined as the degree to which they agree that the items of the questionnaire are appropriate and adequate to measure pattern and problems of wearing the mouthguard, as well as the general perception on the mouthguard.

Fabrication of mouthguards

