For the self-assessment questionnaire of oral impairment, Friedman's test will be used to test for differences between groups because the dependent variable being measured is ordinal. Statistical significance is set at $\alpha = 0.05$. Subsequently, the Wilcoxon signed-rank test will be used for pairwise comparison. Bonferroni adjustment will be done to correct for multiple testing. For part (ii) self-reported frequency of wearing custom-fitted mouthguards, comparisons will be made between T₂, T₃, and T₄. Hence, the adjusted level of statistical significance is set at $\alpha = 0.05/3 = 0.017$. For (iii) problems arise during mouthguard use, and (iv) general perception on a mouthguard, the level of statistical significance is adjusted to $\alpha = 0.05/6 = 0.008$ because of multiple testing between T₁, T₂, T₃, and T₄.

All the recorded speech waveforms will be digitized (at a sampling rate of 22 kHz and 32-bit resolution) and stored on a compact disk. The speech samples collected will be transcribed into the PRAAT software version to assess the acoustic characteristics of the sound via spectrographic analysis. Each speech sample file was given a number which referred to a participant's profile to blind the assessor.

By using spectrogram analysis, mean voice onset time (VOT) values for all phonemes */p b t d /* will be measured in a millisecond. The measurements will be done by manually positioning two cursors in the display of the waveform/spectrogram in the sample file. The beginning and end of a particular measurement of a sound will be judged from both the waveform and spectrogram. The average mean VOT values and voicing duration from the three readings will be obtained for each phoneme.

One-way repeated-measures analysis of variance (ANOVA) will be used to compare the VOT of each phoneme at different time intervals (T_0 , T_1 , T_2 , T_3 , T_4). Statistical significance is set at $\alpha = 0.05$.

7. Flowchart of the study

6 month monitoring period

1. Monitoring logbook
2. 24-hour helpline
3. Modification/replacement of mouthguards (if necessary)

Fourth Speech Performance Recording (T₃)

Fourth Questionnaire Oral Impairment Survey
(T₃)

8. References

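### One speech null hypothesis is tested by four phoneme-wise ANOVAs, each at 0.05, with no correction or decision rule; if any one counts, the false-positive rate is about 10% to 18.5%, not 5%

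*Combined protocol and SAP*

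**What the plan says.** Section 5 (Research hypotheses), item i, is one statement: "Speech performance at various time points is not affected by wearing custom-fitted mouthguard".

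The Data analysis part of section 6 measures "mean voice onset time (VOT) values for all phonemes" /p/, /b/, /t/ and /d/. It then specifies the test: "One-way repeated-measures analysis of variance (ANOVA) will be used to compare the VOT of each phoneme at different time intervals", from T0 to T4, with significance at 0.05. That makes four omnibus tests bearing on one null. Nothing in the section says which phoneme leads, whether the four are combined, or how many must be significant.

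The same section does address multiplicity for the questionnaire: "Bonferroni adjustment will be done to correct for multiple testing". The divisors are 3 (T2, T3, T4) and 6 (T1 to T4), which are the numbers of pairs of time points.

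The sample-size paragraph of section 6 reads: "The assumptions was an effect size of 0.25 with a 5% margin of error". It continues: "The power of the study 80% and there was a total of six repeated measurements". It adds: "Correlation among the repeated measures was set at 0.5". It arrives at 24 players, raised to 30 for drop-out, and describes a single test.

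**The concern.** Speech is the title of the study, its first objective and its first hypothesis. With four chances to reject one null and no rule written down, the team would decide after seeing the data whether one phoneme out of four is enough to say that speech is affected. If it is enough, the stated 0.05 does not describe the error rate of that conclusion. The power statement has the matching gap: it covers one test at 0.05, not a decision drawn from four.

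**Working it through.** **Inputs.** From the documents: four phonemes, alpha 0.05 per test, five time points (T0 to T4), 24 completers or 30 enrolled, effect size 0.25 (read as Cohen's f), correlation over time 0.5, six measurements in the sample-size paragraph. Assumed: any one significant phoneme rejects null i; sphericity holds; the between-phoneme correlation of within-player variation is varied from 0 to 1, because the documents give none (the 0.5 is correlation over time).

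**1. The plan's own figure.** Noncentral F for a one-group repeated-measures ANOVA: lambda = f² × N × m / (1 - rho), with m - 1 and (N - 1)(m - 1) degrees of freedom.

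- m = 6 as stated: 80% power needs N = 19 (power 0.82). N = 24 gives 0.91.
- m = 5 as scheduled: N = 21 is needed. N = 24 gives 0.87.
- m = 4: N = 24 (power 0.82).

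So the stated inputs do not return 24. The drop-out step does reproduce: 24 / (1 - 0.20) = 30. This mismatch is a separate matter and does not affect the error rate below, but it does affect which power figure applies.

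**2. Error rate as planned.** For independent tests, 1 - (1 - 0.05)^4 = 1 - 0.8145 = 18.5%. For correlated tests, simulation of four repeated-measures ANOVAs (24 players, five time points, no true effect, 40,000 runs each):

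| Between-phoneme correlation | At least one p < 0.05 |
|---|---|
| 0 | 18.0% |
| 0.3 | 17.6% |
| 0.5 | 16.3% |
| 0.6 | 14.9% |
| 0.7 | 13.5% |
| 0.8 | 12.0% |
| 0.9 | 10.0% |
| 1 | 5.0% |

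The exact value at zero correlation is 18.5%, so simulation error is about half a percentage point. Results with 30 players are within one point. Relative to 5%, the rate is 10.0 / 5 = 2.0 times at correlation 0.9 and 18.5 / 5 = 3.7 times at 0.

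**3. Error rate with correction.** The first Holm step is 0.05 / 4 = 0.0125. For independent tests, 1 - (1 - 0.0125)^4 = 4.9%; it is lower when the tests are correlated.

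**4. Power for one phoneme.** Same formula. For example, with m = 5 and N = 24, lambda = 0.0625 × 24 × 5 / 0.5 = 15.0 on 4 and 92 degrees of freedom.

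| Measurements | Completers | At 0.05 | At 0.0125 |
|---|---|---|---|
| 5 | 24 | 0.87 | 0.72 |
| 5 | 28 | not needed here | 0.81 |
| 5 | 30 | 0.94 | 0.85 |
| 6 | 24 | 0.91 | 0.79 |
| 6 | 30 | 0.97 | 0.90 |

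If all four phonemes shift by the assumed amount, the power to reject null i at the first Holm step with 24 completers and five visits is about 0.90 or more for between-phoneme correlations up to 0.7, and lower above that.

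**The case against.** The strongest reply is that the plan compares each phoneme, so phoneme-by-phoneme reporting is as compatible with the analysis section as a single verdict. A familywise rate matters only if one phoneme can carry the whole null. It stands that no such rule is written, so the 18.5% is conditional. But the hypothesis is worded once, for speech performance as a whole, and a plan with one null and four tests needs a rule either way.

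Second, all four phonemes come from the same speaker, session and appliance, so high correlation cannot be excluded. That stands too, and it is why the range is carried to 0.9 and beyond. Even at 0.9 the rate is twice nominal.

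Third, this is a small single-arm study, and its problem statement already accepts that a mouthguard can affect speech; the open question is how far speech recovers. This lowers the severity, but does not remove the problem. If one phoneme truly shifts, three tests at 0.05 remain, with a chance of at least one false phoneme claim of 1 - 0.95^3 = 14.3% if independent.

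A reader might also infer that speech is held to a looser standard than the questionnaire. The documents do not support that. The Bonferroni divisors there cover only the follow-up comparisons between time points. The Friedman omnibus test is itself at 0.05, like the VOT ANOVA, and nothing is corrected across questionnaire items either.

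**Conclusion.** The point holds: null i is tested four times at 0.05 with no primary phoneme, correction or decision rule. If any one significant phoneme rejects it, the false-positive rate is about two to nearly four times the stated 5%: 18.5% under independence, about 13.5% at a between-phoneme correlation of 0.7, 10% at 0.9. It approaches 5% only as the correlation approaches 1.

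This rests on the any-one-phoneme reading, on a correlation that the documents do not give, and on sphericity. The plan states no sphericity correction; a departure could raise each test above 5% and was not modelled.

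It would go too far to say that the plan commits the team to rejecting null i on a single phoneme, or that one error rate in this range is established. Severity: should be fixed.

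**What to change.** In the Data analysis part of section 6, after the VOT ANOVA, add: *The four phoneme-wise time tests form one family for null hypothesis i. They are tested by Holm's procedure at familywise alpha 0.05 (ordered p-values against 0.0125, 0.0167, 0.025 and 0.05), and null i is rejected only if the smallest p-value is below 0.0125.* The thresholds apply to unadjusted p-values, so nothing is corrected twice.

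In the sample-size paragraph, first reconcile the six measurements with the five time points. Then state that the calculation is for a single phoneme test at 0.05, and give the power at 0.0125 for the number of visits actually planned. For five visits this is 0.72 with 24 completers, 0.81 with 28 and 0.85 with 30 (no drop-out). For six measurements it is 0.79 with 24 and 0.90 with 30.

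A multivariate test across phonemes would also be valid. If the sponsor wants only phoneme-specific conclusions, hypothesis i should be reworded to say so and the overall claim dropped.

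Cost: a short addition and a less favourable power figure, with no extra data or players. The real loss arises when only one phoneme is affected: power falls from 0.87 to 0.72 with 24 completers and five visits. The rule must be fixed before results are seen, because one chosen afterwards cannot restore the 5%.
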